3.1.5 Safety evaluation methods

If it is not possible to follow up at the clinical trial center according to the visit arrangement due to the epidemic, the clinical examination can be examined by other tertiary hospitals, and the test results will be transmitted back to the clinical trial center for evaluation; The carrier of imaging data in the outer hospital is not limited, and it is necessary to ensure that the imaging department of the center can be opened and read.

3.1.5.1 The main safety evaluation indicators and the methods and time selection of their evaluation, recording and analysis

(1) CTCAE 3 toxicity ratio

Reason for selection: According to the Guidelines for the Technical Review of Clinical Evaluation of Proton Carbon Ion Therapy System (CFDA Circular No. 4 of 2018), if the proportion of CTCAE grade 3 acute toxic reactions exceeds 5%, it is considered as a clinical trial failure, so it is selected The proportion of CTCAE grade 3 toxicity is used as the main safety evaluation index, and CTCAE is a commonly used safety evaluation standard in radiation oncology, which is widely recognized and applied by clinicians.

Indicator definition: Proportion of subjects with grade 3 toxicity during the trial cycle.

Metric type: Qualitative.

Data collection time: the entire clinical trial cycle.

Evaluation time: 3 months \pm 7 days after the last treatment.

Evaluation methodology: Investigators recorded AEs that occurred during the clinical trial cycle and graded them according to CTCAE V5.0.

Calculation formula: proportion of CTCAE grade 3 toxicities = (number of subjects with CTCAE grade 3 toxicity in the test cycle) / total number of subjects \times 100%.

Judging criteria: See CTCAE V5.0 for details.

(2) CTCAE Grade 4 and 5 toxicity ratio

Reason for selection: According to the Guidelines for the Review of Clinical Evaluation Technologies of Proton Carbon Ion Therapy System (CFDA Circular No. 4 of 2018), CTCAE grade 4 and 5 toxicities are considered to be clinical trial failures, so 4 is selected The proportion of grade 5 and grade 5 toxicity reactions is used as a safety evaluation index, and CTCAE is a commonly used safety evaluation standard in radiation oncology, which is widely recognized and applied by clinicians.

Indicator definition: Proportion of subjects with toxicity of grade 4 and 5 during the trial cycle.

Metric type: Qualitative.

Data collection time: the entire clinical trial cycle.

Evaluation time: 3 months \pm 7 days after the last treatment.

Evaluation methodology: Investigators recorded AEs that occurred during the clinical trial cycle and graded them according to CTCAE V5.0.

Formula: Proportion of CTCAE grade 4 and 5 toxicities = (number of subjects with CTCAE grade 4 and 5 reactions in the test cycle) / total number of subjects \times 100%

Judging criteria: See CTCAE V5.0 for details.

3.1.5.2 Secondary safety evaluation indicators and their methods and time selection for evaluation, recording and analysis

(1) CTCAE grade 1 and 2 toxicity ratio

Reason for selection: The proportion of CTCAE grade 3~5 toxicity reactions 3 months after the end of the last treatment was the main safety evaluation index, and the proportion of CTCAE grade 1 and grade 2 toxicity reactions was used as a secondary safety evaluation index for auxiliary evaluation.

Indicator definition: Proportion of subjects with grade 1 and 2 toxicity during the trial cycle.

Metric type: Qualitative.

Data collection time: the entire clinical trial cycle.

Evaluation time: 3 months \pm 7 days after the last treatment.

Evaluation methodology: Investigators recorded AEs that occurred during the clinical trial cycle and graded them according to CTCAE V5.0.

Calculation formula: proportion of CTCAE grade 1 and 2 toxicities = (number of subjects with CTCAE grade 1 and 2 toxicities in the test cycle) / Total number of participants \times 100%.

Judging criteria: See CTCAE V5.0 for details.

(2) Laboratory tests

Reason for selection: According to the Guidelines for Technical Review of Clinical Evaluation of Proton Carbon Ion Therapy System (CFDA Circular No. 4 of 2018), changes in clinical symptoms and signs should be recorded for clinical manifestations, tumor improvement (imaging examinations, laboratory test data), etc., and comprehensive analysis should be carried out. At the same time, it is a routine safety monitoring index for medical device clinical trials.

Data collection and evaluation time: screening period, treatment period 1st day per week (Monday to Sunday is regarded as 1 calendar week, each natural week on the day of the first treatment), before treatment or -1 day (blood count only), 3 days after the end of the last treatment, 1 month \pm 7 days (except coagulation routine), 2 months \pm 7 days (except coagulation routine), 3 months, \pm 7 days (except coagulation routine).

Evaluation items: blood routine, coagulation routine, urine routine, liver function, kidney function.

Evaluation method: Laboratory tests are performed and the investigator judges clinically significant changes in laboratory indicators (before and after radiotherapy).

(3) ECOG grading of physical status

Reason for selection: According to the Guidelines for the Review of Clinical Evaluation Technologies of Proton Carbon Ion Therapy System (CFDA Circular No. 4 of 2018), the follow-up of subjects should include safety and efficacy evaluation. The general condition of the subjects is recommended to be evaluated using the internationally accepted scoring method.

Data collection time and evaluation time: screening period, treatment period on the first day of each week (every Monday to Sunday is regarded as 1 calendar week, each natural week on the day of the first treatment) before treatment or -1 day, 3 days after the end of the last treatment, 1 month \pm 7 days, 2 months \pm 7 days, 3 months, \pm 7 days.

Evaluation method: ECOG physical performance status was graded and reported by the investigator to report clinically significant changes in the test results (before and after radiotherapy).

(4) Tumor recurrence rate

Reason for selection: According to the Guidelines for the Review of Clinical Evaluation Technologies of Proton Carbon Ion Therapy System (CFDA Circular No. 4 of 2018), the clinical trial summary report still needs to be submitted 6 months, 1 year and 2 months after treatment The situation in years and 5 years is summarized, including the tumor recurrence rate. Therefore, an adjuvant analysis of tumor recurrence rate was also added to short-term follow-up. At the same time, it is a common indicator for the safety evaluation of tumor treatment, and is widely recognized and applied by clinicians.

Definition of indicators: The tumor recurrence rate is the ratio of the number of subjects with tumor recurrence to the total number of subjects. Tumor recurrence refers to tumors that are clinically controlled after radiation therapy and regrow after a period of time, in the same nature as the primary tumor. Clinically referred to recurrence mostly refers to local recurrence, such as remnant organs, irradiation fields, and affected adjacent organs. Prostate cancer recurrence refers to biochemical recurrence and PET-CT is required to confirm tumor metastasis to lymph nodes or distant metastases.

Metric type: Qualitative.

Data collection time: screening period, 1 month \pm 7 days, 3 months, \pm 7 days after the last treatment.

Evaluation time: 3 months \pm 7 days after the last treatment.

Evaluation method: The changes in tumor CT or MRI imaging before and after treatment were evaluated by an independent imaging review panel according to RECIST 1.1. At 3 months of radiographic evaluation, if PD is found, PET-CT is required to confirm it.

Calculation formula: tumor recurrence rate = number of subjects with tumor recurrence / total number of subjects \times 100%.

Criteria: See RECIST 1.1 for details. At the time of 3-month imaging evaluation, if the patient is found to have PD, PET-CT examination is required to confirm it, if progress is confirmed, it is recorded as PD, if progress cannot be confirmed, it may be false progression, and it is recorded as SD. If prostate cancer does not have biochemical recurrence, PET-CT examination is not required, and there is no metastasis by default, which is regarded as tumor control, and if biochemical recurrence occurs, it is regarded as tumor not controlled, and PET-CT is required to confirm tumor metastasis.

Note: Participants who discontinued the trial for any reason (other than loss to follow-up) before the end of radiotherapy were considered to have no oncological disease control. Disease site evaluation uses the same approach as baseline, including

consistent contrasted/non-contrast scans and prompt scanning. If changes are needed, the case must be discussed with a radiologist to determine whether an alternative approach is possible. If not, the objective situation in the future is unclear.

(5) Adverse event rate

Reason for selection: Routine safety monitoring indicators for clinical trials of medical devices.

Indicator definition: Adverse events are adverse medical events that occur during clinical trials, whether or not related to a device.

Metric type: Qualitative.

Data collection time: the entire clinical trial cycle.

Evaluation time: 3 months \pm 7 days after the last treatment.

Evaluation method: The investigator recorded all AEs that occurred.

Calculation formula: adverse event rate = number of subjects with adverse events in this group / total number of subjects in this group \times 100%.

(6) Serious adverse event rate

Reason for selection: Routine safety monitoring indicators for clinical trials of medical devices.

Definition: Serious adverse events are those that occur in the course of a clinical trial that result in death or serious deterioration of health, including fatal illness or injury, permanent defects in body structure or function, requiring hospitalization or prolonged hospital stay, or requiring medical or surgical intervention to avoid permanent defects in body structure or body function; Events that lead to fetal distress, fetal death, or congenital anomalies or birth defects.

Metric type: Qualitative.

Data collection time: the entire clinical trial cycle.

Evaluation time: 3 months \pm 7 days after the last treatment.

Evaluation methodology: The investigator recorded all SAEs that occurred.

Calculation formula: Serious adverse event rate = number of subjects with serious adverse events in this group / total number of subjects in this group \times 100%.

(7) Incidence of device defects

Reason for selection: Routine safety monitoring indicators for clinical trials of medical devices.

Definition of indicators: refers to the unreasonable risk that medical devices may endanger human health and life safety under normal use during clinical trials, such as crash.

Metric type: Qualitative.

Time of data collection: during treatment.

Evaluation time: After the last treatment was completed.

Evaluation methodology: The investigator recorded all device defects that occurred.

Calculation formula: incidence of device defects = number of occurrences of device defects / number of times of device use $\times 100\%$.

4 Statistical considerations

4.1 Statistical design, methods, and analytical protocols

This study was a prospective, two-center, single-group target value trial.

All statistical analysis methods are described in detail in the statistical analysis plan. A first draft of the statistical analysis plan is formed after the protocol and eCRF are finalized and will be finalized prior to database locking.

4.2 Sample size calculation

4.2.1 Total sample size

This clinical trial intends to enroll 47 subjects. The sample size determination process is as follows:

This clinical study is designed for clinical verification of a single group of target values, and the tumor disease control rate, the main effectiveness evaluation index, is used as the basis for sample size estimation. According to the Guidelines for the Review of Clinical Evaluation Technologies of Proton Carbon Ion Therapy System (CFDA Circular No. 4 of 2018), the target value is set at 80%, and the bilateral significance level is 0.05, and the power degree 80%, applying the sample size estimation professional software PASS 15.0, calculated by the above parameters, the test group needs a sample size of at least 42 cases. Considering that about 10% of cases may be dropped or lost to follow-up during clinical validation, the sample size of the experimental group was expanded to 47 cases.

4.3 The level of significance and power of clinical trials

The significance level α (bilateral) = 0.05, and the power was 80%.

4.4 Expected shedding rate

In the sample size estimation process, the expected shedding rate is 10%.

This dropout rate refers to the proportion of participants who ultimately could not be included in the primary analysis. Shedding subjects are subjects who have been identified by the investigator as having serious protocol deviations. May include, but is not limited to, the following: the subject violates the inclusion criteria; Participants were not treated with experimental devices; Participants used concomitant medications/devices that are prohibited by the protocol; lack of data on key evaluation indicators; Participants did not obtain any data, etc.

4.5 Criteria for passing/failing clinical trial results

The target value of the main effectiveness evaluation index (tumor disease control rate) of the trial was 80%, and if the lower limit of the 95% confidence interval of the test results was greater than 80%, the tumor disease control rate of the experimental group reached the target.

If the main safety evaluation index of the trial (the proportion of CTCAE grade 3 toxic reactions) is greater than 5%, the clinical trial fails.

If the trial has CTCAE grade 4 and 5 toxicity, the clinical trial fails.

4.6 Criteria and reasons for terminating trials on statistical grounds

No interim analysis was performed in this study and therefore criteria for termination of the trial for statistical reasons were not established.

4.7 Statistical methods of data, together with methods of dealing with missing, unused or erroneous data and irrational data

4.7.1 Data statistical methods

Statistical analysis with SAS 9.4 software.

All data are described statistically, including demographics, baselines, all efficacy measures, and all safety data. The measurement data give the mean, standard deviation, minimum, maximum, median, 25th quantile and 75th quantile; The counting data gives the frequency and the corresponding percentage.

Effectiveness Analysis:

The number and percentage of cases achieving DCR were calculated, and the Clopper-Pearson method was used to calculate the 95% confidence interval for tumor disease control rate. ORR was calculated and the Clopper-Pearson method was used to calculate the objective response rate 95% confidence interval. Descriptive statistics on the percentage change from baseline of the sum of the longest diameter (SLD) of the measurable tumor. The Waterfall Chart was made by the maximum percentage reduction in SLD per patient compared to the screening period.

The *Kaplan-Meier* method was used to calculate the median duration of response, median progression-free survival, median survival, and overall survival, and plotted *K-M* curves (long-term follow-up data).

For tumor markers, compare and evaluate the changes before and after treatment, and give clinical evaluation [no clinical significance, clinically significant (tend to normal), clinically significant (tend to be abnormal), not checked].

Safety Analysis:

Descriptive statistics were used to classify organ systems in MedDRA medical terms, and the incidence, occurrence, and severity of adverse events, adverse reactions, and serious adverse events were summarized.

Laboratory indicators, ECOG physical status classification and other safetyrelated indicators were compared and evaluated before and after treatment, and clinical evaluation ([no clinical significance, clinically significant (tending to normal), clinically significant (tending to abnormal), not checked], CTCAE grade evaluation before and after treatment cross-table.

4.7.2 Missing, unused, or erroneous data (including mid-exit and evacuation) and unreasonable data

All missing, unused or erroneous data (including mid-exit and withdrawal) and unreasonable data will be discussed and finalized by investigators and biostatisticians during the blinding review phase. The basic statistical principles of these data processing are as follows:

- (1) Describe the details of each shedding case;
- (2) Missing data from baseline, which can not be estimated;
- (3) The missing values of DCR and primary safety evaluation indicators
 (proportion of CTCAE grade 3 toxicities, proportion of CTCAE grade
 4 and 5 toxicities) at 3 months after the end of treatment can be estimated using worst-case scenarios.
- (4) The missing values of qualitative secondary effectiveness evaluation indicators ORR, DCR and long-term follow-up effectiveness evaluation indicators can be estimated using worst-case scenarios;
- (5) The missing values of quantitative secondary efficacy evaluation indicators DOR, tumor markers, product ease assessment and long-term follow-up effectiveness evaluation indicators were not estimated.
- (6) Erroneous, unreasonable data (out-of-range data and data that contradicts other data or indicators of the study protocol) can be treated as missing values;
- (7) Worst-case estimates are used for missing values for all minor safety indicators;

- (8) The sensitivity analysis of the main effectiveness evaluation indicators and main safety evaluation indicators after treatment was carried out in the whole analysis center.
- (9) The sensitivity analysis of all secondary effectiveness evaluation indicators after treatment was carried out in the whole analysis center.
- (10) For all secondary safety evaluation indicators after treatment, sensitivity analysis was carried out in the security dataset.

4.8 Procedures for reporting deviations from the original statistical plan

Under normal circumstances, only the statistical analysis content agreed in advance included in the statistical analysis plan can be presented in the clinical trial report of this trial. The increased demand for statistical analysis for various uncertain reasons is only exploratory analysis.

4.9 Selection criteria and rationale for participants included in the analysis

Full Analysis Set (FAS): All subjects who received at least 1 investigational device treatment and at least one post-baseline observation data will be enrolled in FAS, according to the basic principles of intention-to-heart analysis. FAS will be used as the primary population for baseline data and sensitivity analysis for validity evaluation. Participants may only be excluded in very limited circumstances, including when important inclusion criteria are violated and no observational data are available after enrollment.

Compliant protocol set (PPS): is a subset of FAS, defined as subjects who have measurable lesions at baseline and have completed at least one assessment of primary efficacy indicators after baseline. PPS will be the primary population for the effectiveness evaluation of this study.

Safety dataset (SS): all participants who received at least 1 study device treatment and at least one safety assessment. SS will be the primary population for safety analysis in this study.

The assessment of baseline characteristics will use the full set of analyses; The evaluation of effectiveness will use both the full analysis set and the conforming protocol set; Security analysis uses security datasets.

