3.1.2 Choice of trial method and justification

This trial was designed using the prospective, two-center, single-group target value method.

- (1) Prospective study: Adopt a research approach that traces from the present to the future. Prospective studies can establish cause and effect; There are unified diagnosis, detection and evaluation standards for the obtained data, so the data processing is controllable.
- (2) Two centers: Select 2 clinical trial institutions to carry out the clinical trial. More cases than single-center trials can be obtained in the same amount of time, thus shortening the duration of clinical trials.
- (3) Single-group target value method: Because the same device of the experimental medical device is radioactive and difficult to obtain, the existing treatment method is not feasible due to objective conditions, so the single-group target value method is adopted. Moreover, the applicable population and main evaluation indicators of experimental medical devices can be fully defined and relatively stable; The main evaluation index adopts the effective rate mentioned in the "Guidelines for the Technical Review of Clinical Evaluation of Proton Carbon Ion Therapy System" (CFDA Circular No. 4 [2018]), which is relatively objective and reproducible. According to the Guidelines for the Technical Review of Clinical Evaluation of Proton Carbon Ion Therapeutic response rate for experimental medical devices should be at least 80%, and the expected value should be 95%. Among them, the effective definition is: CR+PR+SD (complete response CR, partial response PR, disease stable SD), which is basically consistent with the definition of tumor disease control rate in this clinical trial. Therefore, no control group was set up in this clinical trial, and the single-group target value method was used to evaluate whether the tumor disease control rate reached the target value (80%) and the main safety evaluation index CTCAE 3 when ProBeam was used in

radiotherapy for tumor patients Whether the proportion of grade toxicities is less than acceptable (5%) and whether the proportion of CTCAE grade 4 and 5 toxicities is acceptable (0%).

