3.1.3.1 Enrollment time

The investigators obtained the informed consent of the participants and signed the ICF, which was then screened according to the inclusion criteria. If the patient meets all the inclusion criteria of this trial and does not meet any of the exclusion criteria,

the case is included in this trial, and the time of enrollment of the subject is used as the treatment on the day of the first treatment, and a unique enrollment number is obtained in the order of enrollment.

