Evaluation method: The changes in tumor CT or MRI imaging before and after treatment were evaluated by an independent imaging review panel according to RECIST 1.1. At 3 months of radiographic evaluation, if PD is found, PET-CT is required to confirm it.

Calculation formula: DCR = number of disease control subjects / total number of subjects × 100%.

Criteria: See RECIST 1.1 for details. At the time of 3-month imaging evaluation, if the patient is found to have PD, PET-CT examination is required to confirm it, if progress is confirmed, it is recorded as PD, if progress cannot be confirmed, it may be false progression, and it is recorded as SD. If prostate cancer does not have biochemical recurrence, PET-CT examination is not required, and there is no metastasis by default, which is regarded as tumor control, and if biochemical recurrence occurs, it is regarded as tumor not controlled, and PET-CT is required to confirm tumor metastasis.

Note: Participants who aborted the trial for any reason (except loss to follow-up) before the end of the last radiation therapy were considered to have disease progression (PD) or were not controlled. Disease site evaluation uses the same approach as baseline, including consistent contrasted/non-contrast scans and prompt scanning. If changes are needed, the case must be discussed with a radiologist to determine whether an alternative approach is possible. If not, the objective situation in the future is unclear.

3.1.4.2 Secondary effectiveness evaluation indicators and their methods and timing of evaluation, recording, analysis

(1) Objective response rate (ORR).

Reason for selection: The Guidelines for the Review of Clinical Evaluation Technologies of Proton Carbon Ion Therapy Systems (CFDA Circular No. 4 [2018]) recommends the use of the latest version of the commonly used evaluation criteria for radiation oncology as the clinical trial evaluation criteria, so RECIST 1.1 is used Relevant indicators as effectiveness evaluation criteria; Due to the particularity of the disease, the evaluation method recommended in the relevant diagnosis and treatment guidelines is selected. All of them can directly measure the effect of radiotherapy and are widely recognized and applied by clinicians.

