congenital defects and other events.

Confidential Information Page 7 / 17

Statistical Analysis Plan Version: V1.0
Date: 2022-11-11

Calculation formula: incidence of serious adverse events = number of subjects with serious adverse

events in this group / number of all subjects in this group $\times 100\%$;

• Incidence of device defects

Device defects refer to the unreasonable risk that medical devices may endanger human health and life

safety under normal use during clinical trials, such as crashes.

Calculation formula: incidence of device defects = number of device defects / number of device use

 $\times 100\%;$

3 Statistical analysis set

The following analysis sets were defined in this trial for statistical analysis.

Full Analysis Set (FAS): According to the basic principles of intention-to-treat analysis, all participants who

received at least one treatment with an investigational device and at least one post-baseline observational data

will be included in the FAS. FAS will be used as the main population for the baseline data and effectiveness

evaluation sensitivity analysis of this study. Exclusion is only possible in very limited circumstances, including

cases where important enrollment criteria have been violated and no observational data have been available after

enrollment.

Per-Protocol Set (PPS): is a subset of FAS and refers to subjects with measurable lesions at baseline who

have completed at least one primary efficacy measure assessment after baseline. PPS will be the main population

in the evaluation of the effectiveness of this study.

Safety Set (SS): All participants who received at least one treatment with an investigational device and had

at least one safety evaluation. SS will be the primary population for safety analysis in this study.

The baseline characteristics will be assessed using the full analysis set, the effectiveness will be assessed

using both the full analysis set and the conformance set, and the safety analysis will use the safety dataset.

4 data processing

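### The FAS drops treated subjects with no post-baseline observation, including early stoppers whom the protocol already scores as not controlled, so the FAS disease control rate is biased upward

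*Protocol*

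**What the plan says.** Protocol 4.9 gives the FAS two entry conditions: "All subjects who received at least 1 investigational device treatment and at least one post-baseline observation data will be enrolled in FAS". SAP section 3 has the same two: subjects who "received at least one treatment with an investigational device and at least one post-baseline observational data". Both texts say the set follows intention-to-treat principles, and both mention absence of data after enrolment among the limited grounds for exclusion.

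Three other provisions bear on this:

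- **Enrolment.** Protocol 3.1.3.1 dates enrolment to the first treatment: "the time of enrollment of the subject is used as the treatment on the day of the first treatment". Protocol 3.1.3.2 expects all 47 enrolled subjects to be treated.
- **Outcome by rule.** The note in protocol 3.1.4.1, matched in the protocol summary, assigns an outcome to early stoppers: "aborted the trial for any reason (except loss to follow-up) before the end of the last radiation therapy were considered to have disease progression (PD". The same sentence gives lack of control as the alternative label. No scan is needed for this. The disease control rate (DCR) is divided by the total number of subjects.
- **Roles of the sets.** The PPS is a subset of the FAS, requires measurable disease and at least one post-baseline primary efficacy assessment, and is the main efficacy population. The FAS serves the sensitivity analysis. Under SAP 5.6 the PPS result leads if the two disagree.

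The pass rule in protocol 4.5 is a lower 95% confidence limit above 80%. Protocol 4.7.1 and SAP 5.4.1 specify the Clopper-Pearson method.

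**The concern.** A post-baseline data condition is usually defended on the ground that a subject without data has no outcome to analyse. That defence does not cover every subject here. Someone who starts treatment, withdraws in the first days and leaves no later record has been assigned a failure by the endpoint definition. The FAS definition then removes that person, and nesting removes them from the PPS as well. The failure is assigned in one section and counted in no efficacy set.

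For these subjects the exclusion runs in one direction. A single-arm trial against a fixed target has no control arm in which a similar loss could offset it. What is at stake is the credibility of the FAS result: it is the only planned check on a more selective PPS, and it should not lose the earliest failures.

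**Working it through.** **Inputs.** Target 80%, two-sided 5% level and 80% power ("the target value is set at 80%, and the bilateral significance level is 0.05, and the power degree 80" per cent, protocol 4.2.1). Expected DCR from protocol 3.1.2: "the expected value should be 95" per cent. Evaluable number 42, enrolled number 47 (protocol 4.2.1). Pass rule: Clopper-Pearson lower limit above 80%.

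**1. The plan's own figure.** With the normal approximation,

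n = [(1.960·√(0.80·0.20) + 0.842·√(0.95·0.05)) / 0.15]² = 41.6, rounded up to 42.

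Allowing for 10% dropout, 42/0.90 = 46.7, rounded up to 47. Both stated numbers are reproduced.

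**2. How many failures the rule tolerates.** The lower limit for x controlled out of n is the 2.5% quantile of Beta(x, n − x + 1).

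- n = 47: 44/47 gives 82.46% (above 80%); 43/47 gives 79.62% (below).
- n = 46: 43/46 gives 82.10% (above); 42/46 gives 79.21% (below).

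At both sizes three failures pass and four do not. The same holds at every n from 42 to 47.

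**3. One early stopper at the margin.** Take 47 treated and four not controlled, one of whom stopped early with no later data.

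- All treated subjects counted: 43/47 = 91.5%, lower limit 79.6%. The FAS result misses the target.
- FAS as written: 43/46 = 93.5%, lower limit 82.1%. The FAS result meets it.

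The same reversal occurs for each treated total from 42 (38/42, 77.38%, becomes 38/41, 80.08%) to 47.

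**4. Effect on the FAS pass probability.** Let e be the share of treated subjects who stop early with no post-baseline data, all scored as failures. The documents give no value, so e is an assumption. With a true all-treated DCR of exactly 80%, the control rate among those left in the FAS is 0.80/(1 − e). The pass probability is summed over a binomial number of exclusions from 47, using the pass count for each remaining n.

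| e | expected number dropped (47·e) | FAS pass probability |
|---|---|---|
| 0 | 0 | 0.9% |
| 1% | 0.47 | 1.4% |
| 2% | 0.94 | 2.1% |
| 2.5% | 1.2 | about 2.5% |
| 4% | 1.9 | 4.4% |

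The nominal one-sided level is 2.5%.

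**5. Does anything bring these subjects back?** Worst-case estimation in protocol 4.7.2 is optional and does not override set membership. The FAS sensitivity analysis in SAP 5.4.1 carries the worst observation forward, which requires an observation. SAP 2.1.1 does not repeat the rule that an early stop counts as a failure. SAP 4.3 says missing primary values in the FAS sensitivity analysis are not filled, whereas SAP 5.4.1 says they are.

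**The case against.** A reader might infer that one such subject could turn a failed trial into a successful one. The documents do not support that. The PPS is the main efficacy population and prevails on conflict (SAP 5.6), and its own requirement of a completed primary assessment omits the same subject. Deleting the FAS clause alone would leave the PPS result where it is and give a discordant FAS result to discuss. This objection stands, and it limits the point to the FAS result.

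The affected group is probably close to empty. The type of observation is not specified; blood counts and ECOG status are scheduled weekly, and adverse events are collected throughout. A subject known to have withdrawn will often have some record. This also stands, although the vagueness leaves it unclear what qualifies.

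It would be too strong to say that the clause removes only failures. Subjects lost to follow-up are exempt from the scoring rule and have no assigned outcome. The one-directional bias applies only to the other early stoppers.

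A reader might extend the argument to the Safety Set, which requires a safety assessment. No direction of bias is shown there: on observed data, removing a subject without recorded toxicity raises the toxicity proportion, which works against the sponsor.

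Safeguards exist. Exclusions are settled before database lock (SAP 5.3.2), and withdrawals and their reasons are reported (SAP 5.3.1). These let a reader see the omission but do not correct the estimate.

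**Conclusion.** The point holds for the FAS result. The clause can remove only treated subjects, and those who stop before radiotherapy ends, other than by loss to follow-up, and leave no later data are failures under the protocol's own endpoint. Omitting them biases the FAS DCR upward.

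The effect is small in expectation. The FAS pass probability at a true DCR of 80% stays below 2.5% unless about 2.5% of treated subjects are dropped this way, which is more than one expected subject in 47. At the margin one subject is enough to reverse the FAS result. That reversal concerns the confidence-limit rule; on the single-sample chi-square test that the SAP adds, 43/47 already differs from 80% (z = (0.9149 − 0.80)/√(0.16/47) = 1.97).

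The trial's verdict would change only if the FAS were also made decisive. The size rests on the assumed share e and on how the undefined term for post-baseline data is read.

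**What to change.** - In protocol 4.9 and SAP section 3, define the FAS as all enrolled subjects treated at least once. Delete the post-baseline data condition and the matching exclusion ground of no data after enrolment.
- Add the protocol's rule to SAP 2.1.1 and 5.4.1: stopping before the end of radiotherapy, except by loss to follow-up, counts as not controlled. Without this the SAP would treat the restored subjects as missing.
- Reconcile SAP 4.3 (primary values not filled) with SAP 5.4.1 (worst observation carried forward). In the FAS sensitivity analysis, score as not controlled any treated subject with no observation to carry forward, in line with the worst-case option in protocol 4.7.2.
- Leave the Safety Set definition as it is.

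The cost is a few sentences in two documents and no new data collection. The FAS DCR may become slightly less favourable, by at most the few subjects concerned. The change should be made before database lock, since protocol 4.8 treats later additions as exploratory.
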